3.6 Exploratory Analyses

3.6.1 Healthcare Resource Utilization (HRU)

For each season, the following summaries will be provided using the respective ITT population. The Season 1 summaries will also be repeated for each cohort (pre-term, CHD/CLD).

The magnitude of healthcare resource utilization (HRU; as measured by number of admissions to hospitals and duration of stay; number of admissions to the intensive care unit [ICU] and duration of stay; number requiring respiratory support and the duration of use; number requiring supplemental oxygen and the duration of use; number and type of visits to outpatient facilities [outpatient ED, urgent care, outpatient clinic] will be summarized by

treatment group and reported in 3 time periods: through 150 days post 1st dose (on ITT population), after 150 days post dose (on ITT population with Day 151 visit), and through 360 days post dose (on ITT population).

Specifically, the following summary tables by treatment group will be used to report the magnitudes of overall HRU for all medically attended LRTI (protocol defined, non-protocol defined, RSV, non-RSV):

- The number and percent of subjects who have had at least one of the following: hospitalization, ICU admission, requiring respiratory support, requiring supplemental oxygen, or visiting an outpatient facility (for any type of the outpatient facility). Similar summaries will also be provided by respiratory support subtype (CPAP or mechanical ventilation) and the type of outpatient facility. The percentage will be calculated based on ITT population for time interval through 150 days post 1st dose, on ITT population with Day 151 visit for time interval after 150 days post 1st dose, and on ITT population for time interval through 360 days post 1st dose.
- For each of the medical activities listed above, the total number of the activity for a subject who has had at least one respective event in the reporting time-period will be calculated and summarized by treatment group using descriptive statistics (mean, median, standard deviation [SD], minimum, and maximum).
- The total duration of each of the following (in days) will be calculated accumulatively throughout the reporting time-period and summarized by descriptive statistics (mean, median, SD, minimum, and maximum): hospital stay, ICU stay, use of respiratory support, or use of supplemental oxygen for the subjects who had at least one of the corresponding activities.

Duration of each hospitalization will be calculated from the admission or deterioration date to discharge date. If the discharge date is missing because the subject died in the hospital, the duration of that hospital stay will be calculated from admission to the minimum of {Death Date, End-of-Study Date, Data Cutoff Date at the time of Primary Analysis}. Total duration of hospitalization is the cumulated days of each hospital stay throughout the reporting time-period.

Similarly, duration of each ICU admission, use of respiratory support, or use of supplemental oxygen will be calculated from start date to stop date or the end date, and the total duration of each medical intervention for a subject is calculated by summing the duration of all occurrences in the time interval of interest.

In addition to the overall HRU summary, the HRU for medically attended RSV LRTI (Protocol-defined) will be summarized through 150 days post 1st dose, after 150 days post 1st dose, and through 360 days post 1st dose. The same conventions used for the overall summary (eg, patient population included in a specific summary) will be applied for the respective

events and the HRU must occur during the event being summarized. Only the subjects with protocol-defined medically attended RSV LRTI will be included in the summary.

In addition, the number of pre-specified OTC medication (analgesics/antipyretics) use will be summarized by treatment group and overall through one week after dosing. The number of pre-specified prescription medication (systemic antibacterial agents) use; the number of anti-wheezing medication use, and the number of antiviral therapy use will be summarized by treatment group and overall through 150 days post 1st dose. The Anatomical Therapeutic Chemical (ATC) codes for these medications will be provided in a separated file provided by medical monitor prior to DBL for primary analysis.

The number and percentage of subjects with pre-specified prescription medications (systemic antibacterial agents) use through 150 days post dose will be provided. The number of use per subject (for those with the medication use) will be summarized through 150 days post dose using descriptive statistics (mean, median, SD, minimum, and maximum) by treatment group and for all subjects combined.

The number and percentage of subjects with pre-specified OTC medications (analgesics/antipyretics) use within one week after dosing will be provided. The number of use per subject (for those with the medication use) will be summarized using descriptive statistics (mean, median, SD, minimum, and maximum) by treatment group and for all subjects combined. The same summaries will be repeated for subjects with any co-administerrated routine childhood vaccination (J07) within one week of dosing.

The number and percentage of subjects with anti-wheezing medications use through 150 days post dose will be provided. The number of use per subject (for those with the medication use) will be summarized through 150 days post dose using descriptive statistics (mean, median, SD, minimum, and maximum) by treatment group and for all subjects combined.

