4.1.2 Inclusion Criteria

Subjects must meet all of the following criteria:

- 1 For the preterm cohort (excluding subjects with CLD or hemodynamically significant CHD): preterm infants in their first year of life and born ≤ 35 weeks 0 days GA eligible to receive palivizumab in accordance with national or local guidelines, including those with:
 - (a) Uncomplicated small atrial or ventricular septal defects or patent ductus arteriosus, *or*
 - (b) Aortic stenosis, pulmonic stenosis, or coarctation of the aorta alone
- 2 For the CLD/CHD cohort:
 - (a) Subjects with CLD - infants in their first year of life and a diagnosis of CLD of prematurity requiring medical intervention/management (ie, supplemental oxygen, bronchodilators, or diuretics) within the 6 months prior to randomization
 - (b) Subjects with CHD - infants in their first year of life and documented, hemodynamically significant CHD (must be unoperated or partially corrected CHD)
Note: Infants with hemodynamically significant acyanotic cardiac lesions must have pulmonary hypertension (≥ 40 mmHg measured pressure in the pulmonary artery) or the need for daily medication to manage CHD
- 3 Infants who are entering their first RSV season at the time of screening
- 4 Written informed consent and any locally required authorization (eg, Health Insurance Portability and Accountability Act in the USA, EU Data Privacy Directive in the EU) obtained from the subject's parent(s)/legal representative(s) prior to performing any protocol-related procedures, including screening evaluations
- 5 Subject's parent(s)/legal representative(s) able to understand and comply with the requirements of the protocol including follow-up and illness visits as judged by the investigator
- 6 Subject is available to complete the follow-up period, which will be 1 year after Season 1/ Dose 1 for subjects without CLD/CHD, or 1 year after Season 2/Dose 1 (or last replacement dose as applicable for CHD) for subjects with CLD/CHD

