Table 7 Criteria for Meeting the Protocol-defined Endpoint of Medically Attended RSV LRTI - Subjects Without Underlying Lung Disease

RSV	Lower Respiratory Tract	Medical Significance
RSV Confirmed: 
 Positive by central laboratory real-time RT-PCR assay 	Documented physical examination findings localizing to lower respiratory tract: 
 Rhonchi Rales Crackles Wheeze 	Objective measures of clinical severity: 
 Increased respiratory rate Hypoxemia Acute hypoxic or ventilatory failure New onset apnea Nasal flaring Retractions Grunting Dehydration due to respiratory distress

LRTI = lower respiratory tract infection; RSV = respiratory syncytial virus; RT-PCR = reverse transcriptase-polymerase chain reaction.

Note: One item from each column is required to meet the protocol-defined endpoint of medically attended RSV LRTI.

For subjects with underlying lung disease (CLD or CHD):

To meet the protocol-defined endpoint of medically attended RSV LRTI, subjects with signs of LRTI must have documented at least one new or worsened physical examination finding of rhonchi, rales, crackles, or wheeze AND at least one of the following clinical signs (see [Table 8](#)):

- Increase in baseline respiratory rate by $\geq 20\%$ at rest and that rate is greater than the age-based criteria established for children with no underlying lung disease (age: < 2 months, ≥ 60 breaths/min; 2 to 6 months, ≥ 50 breaths/min; > 6 months, ≥ 40 breaths/min), OR
- Hypoxemia (O_2 saturation $< 95\%$ in room air or O_2 saturation drop of 5 percentage points from baseline in children with baseline O_2 saturation $< 95\%$ in room air, or acute documented need for supplemental O_2 or increased O_2 requirement compared with baseline), OR
- Clinical signs of severe respiratory disease (eg, acute hypoxic or ventilatory failure, new onset apnea, nasal flaring, intercostal, subcostal or supraclavicular retractions, grunting) or dehydration secondary to inadequate oral intake due to respiratory distress (need for intravenous fluid), OR
- Prescription of new or increased (from baseline) dose of medications including bronchodilators, steroids, diuretics, cardiac medications

Table 8 Criteria for Meeting the Protocol-defined Endpoint of Medically Attended RSV LRTI – Subjects With Underlying Lung Disease (CLD or CHD)

RSV	Lower Respiratory Tract	Medical Significance

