4.3.6 Healthcare Resource Utilization and Caregiver Burden

Information on HRU and caregiver burden will be collected for all events of medically attended LRTI (see [Table 5](#) and [Table 6](#)). This will include admission to and duration of hospital and intensive care unit (ICU) stay, number of subjects who require respiratory support and supplemental oxygen use, duration of respiratory support and supplemental oxygen use, number and type of outpatient visits (eg, ER, urgent care, outpatient clinic), and the number of prescription and over-the-counter (OTC) medications and their duration of use. Caregiver burden will be assessed through, for example, caregiver missed work days and the subject's absence from day care.

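### SAP 3.6.1 does not separate anti-wheezing and oxygen use already ongoing at baseline from new or increased use, so the CLD/CHD resource-use tables mix the two

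*SAP*

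**What the plan says.** **Anti-wheezing medication.** SAP 3.6.1 states: "The number and percentage of subjects with anti-wheezing medications use through 150 days post dose will be provided". The row is not tied to an LRTI and carries no condition on when the treatment began or whether its dose rose.

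**Oxygen.** The listed measures include the "number requiring supplemental oxygen and the duration of use". For duration the SAP says: "use of respiratory support, or use of supplemental oxygen will be calculated from start date to stop date or the end date". Occurrences are then added up over the reporting interval, with no comparison against the level before the illness.

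**Hospital days.** "Duration of each hospitalization will be calculated from the admission or deterioration date to discharge date". For protocol-defined RSV LRTI, the same section also requires the resource use to coincide with the event being tabulated.

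**Who is enrolled.** For CLD, Protocol 4.1.2 asks for "a diagnosis of CLD of prematurity requiring medical intervention/management (ie, supplemental oxygen, bronchodilators, or diuretics) within the 6 months prior to randomization". Exclusion criterion 5 in Protocol 4.1.3 bars infants on ventilation, CPAP or other mechanical support at randomization. Oxygen without such support is not listed.

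**When resource use is collected.** Protocol 4.3.6: "Information on HRU and caregiver burden will be collected for all events of medically attended LRTI".

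**How the endpoint treats the same issue.** In children with underlying lung disease, the case definition in Protocol 4.3.1.1 compares with baseline. One qualifying item is "Prescription of new or increased (from baseline) dose of medications including bronchodilators, steroids, diuretics, cardiac medications", and its oxygen items likewise refer to a drop or an added need relative to baseline.

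**The concern.** The exploratory objective is to compare resource use between MEDI8897 and palivizumab recipients, and Protocol 3.2.3 presents it as burden from RSV illness. A child on a maintenance bronchodilator is a user from Day 1 in either arm, and nothing that happens on study can change that child's status in an any-use row. A child on home oxygen, if that oxygen is entered at an LRTI, brings a duration that reflects chronic lung disease and not the infection. The case definition guards against this by asking for change from baseline; the resource-use rules do not.

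What is at stake is how the CLD/CHD tables read. SAP 3.6.1 repeats the Season 1 summaries for that cohort, and Season 2 consists only of that cohort. A reader could take similar percentages or similar mean oxygen days as evidence of similar illness burden when much of what is counted was there before the first dose.

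**Working it through.** **Planned figures.** The documents give no planned figure for resource use. The nearest is the expected number of RSV LRTIs (Protocol 4.8.2), which reproduces: 0.06 × 300 = 18 and 0.06 × 600 = 36. At the same 6%, the CLD/CHD cohort (about 100 palivizumab, 200 MEDI8897; Protocol 3.1.1) would give 6 and 12. The protocol warns that rates could be much lower, so durations will rest on few children.

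The chronic-use shares, new-use rates and durations below are assumptions, because the documents give none.

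**A. Any anti-wheezing use, CLD/CHD cohort.** Let b be the share on maintenance treatment at baseline and p the new-use rate among the rest. The tabulated proportion is b + (1 − b)p. The difference between arms is (1 − b)(p_pal − p_MEDI).

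| b | Pal, p = 12% | MEDI8897, p = 6% | Difference (points) | Ratio | Ratio if p = 6% vs 3% |
|---|---|---|---|---|---|
| 0 | 12.0% | 6.0% | 6.0 | 0.50 | 0.50 |
| 10% | 20.8% | 15.4% | 5.4 | 0.74 | 0.83 |
| 20% | 29.6% | 24.8% | 4.8 | 0.84 | 0.90 |
| 40% | 47.2% | 43.6% | 3.6 | 0.92 | 0.96 |

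Example at b = 20%: 0.20 + 0.80 × 0.12 = 0.296; 0.20 + 0.80 × 0.06 = 0.248; 0.248 / 0.296 = 0.84.

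For the whole trial, take CLD/CHD as one third of subjects, with no maintenance use in the preterm cohort. The effective share is then b/3. For b = 10%, 20% and 40%, the ratio reads 0.61, 0.69 and 0.78, and the difference 5.8, 5.6 and 5.2 points.

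**B. Any oxygen, recorded only at an LRTI.** Assume LRTI in 12% against 6%, and acute oxygen in half of those not already on it. The share of LRTI cases with oxygen is s = b + (1 − b) × 0.5, and the arm proportions are 0.12s and 0.06s. The ratio is 0.50 whatever b is. The difference rises from 3.0 points at b = 0 to 4.2 points at b = 40%. This row is not diluted.

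**C. Mean oxygen days among users.** Assume acute means of 5 against 3 days (SD 3), and a share f of users on chronic oxygen recorded as D days. The mean is (1 − f) × acute mean + f × D. The variance is (1 − f)(SD² + acute mean²) + fD² − mean².

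| D | f | Means (days) | Difference | Ratio | Standardized difference |
|---|---|---|---|---|---|
| – | 0 | 5.0 vs 3.0 | 2.0 | 0.60 | 0.67 |
| 30 | 10% | 7.5 vs 5.7 | 1.8 | 0.76 | 0.22 |
| 30 | 30% | 12.5 vs 11.1 | 1.4 | 0.89 | 0.12 |
| 150 | 10% | 19.5 vs 17.7 | 1.8 | 0.91 | 0.04 |
| 150 | 30% | 48.5 vs 47.1 | 1.4 | 0.97 | 0.02 |

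The difference in days moves little. The spread grows so much that it would be invisible among a handful of children.

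**D. Nosocomial stay counted to discharge.** A 7-day RSV illness followed by 7, 30 or 60 further inpatient days is recorded as 14, 37 or 67 days, of which 50%, 19% or 10% are illness. Whether the later days stay in the RSV LRTI table is unclear. The coincidence rule would seem to cut them, while the to-discharge rule and the nosocomial day count in Protocol 4.3.1.1 keep them.

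**The case against.** The strongest reply is that the plan already contains most of what is needed. Oxygen, respiratory support and hospital use are collected at LRTI events only. The RSV LRTI table demands that use coincide with the event. Days before a nosocomial deterioration are excluded. Children on ventilation or CPAP at randomization are not enrolled. Randomization within cohort balances baseline use on average, Season 1 tables are repeated by cohort, and the median is shown beside the mean. The SAP plans no ratio for resource use, only counts, percentages and descriptive statistics by arm, and tests nothing.

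Much of this stands, and it rules out a stronger reading that a reader might infer: that all pre-existing care enters the tables and dilutes every difference between arms. Check B shows one row that is not diluted. Checks A and C show that absolute differences shrink far less than ratios move. Nor do the documents support the inference that the SAP departs from the protocol on nosocomial stays. In Protocol 4.3.1.1, new or increased need defines when the event starts, and the days after that point count, so the SAP's deterioration-to-discharge rule follows it. Entry under the CLD criterion also needs treatment only at some time in the preceding six months, so it does not show how many infants are still treated at Dose 1.

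The reply does not reach the anti-wheezing row, which is tied to no event. Nor does the coincidence rule remove chronic oxygen, which is by its nature present during the illness.

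**Conclusion.** The gap is real but narrow, and minor. As written, the anti-wheezing summary mixes maintenance and new use, and the oxygen durations have no above-baseline rule. Both matter mainly in the CLD/CHD tables.

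On the assumed inputs, an any-use ratio of 0.50 reads 0.74 to 0.92 in that cohort. The absolute difference falls in proportion to the maintenance share: by a tenth or a fifth at b = 10% or 20%, and by 40% only at the top of the range. Across the whole trial it falls from 6.0 to no less than 5.2 points.

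The oxygen result holds only if sites enter chronic home oxygen at an LRTI, which depends on case-report-form instructions not in the documents. If they do, the main effect is noise in the means, not a shift in the difference. No error rate, sample size, or primary or secondary conclusion is affected.

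**What to change.** In SAP 3.6.1:

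1. Split the anti-wheezing summary into two rows: use ongoing at the season baseline, as SAP 3.1 already defines it, and use started or increased after Dose 1 of that season. Name the second as the row for comparing arms.
2. In the LRTI resource-use tables, keep total oxygen and add oxygen that is new or increased over the pre-illness level, with its days limited to the LRTI episode.
3. For protocol-defined RSV LRTI, reconcile the requirement that use coincide with the event with the to-discharge rule and the protocol's nosocomial day count. One way is to show total days and days within the event side by side.

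The cost is SAP wording, some programming and a few extra rows, and the new-use figures will be smaller than the any-use figures. Concomitant medications are recorded from screening (Protocol 4.7 and Table 4), AE onset and stop dates exist, and the case definition already calls for oxygen need and medication change relative to baseline. If medication records do not carry dose, the second anti-wheezing row can be limited to newly started treatment, with a footnote saying so.

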
RSV Confirmed:
 
 Positive by central laboratory real-time RT-PCR assay 	
Documented new or worsened physical examination findings localizing to lower respiratory tract:
 
 Rhonchi Rales Crackles Wheeze 	
Objective measures of clinical severity:
 
 Increased respiratory rate (from baseline) Hypoxemia Acute hypoxic or ventilatory failure New onset apnea Nasal flaring Retractions Grunting Dehydration due to respiratory distress Prescription of new or increased (from baseline) dose of medications including bronchodilators, steroids, diuretics, cardiac medication

CHD = congenital heart disease; CLD = chronic lung disease; LRTI = lower respiratory tract infection; PE = physical examination; RSV = respiratory syncytial virus; RT-PCR = reverse transcriptase-polymerase chain reaction.

Note: One item from each column is required to meet the protocol-defined endpoint of medically attended RSV LRTI.

RSV Hospitalization

An RSV hospitalization is defined as either (1) a respiratory hospitalization with a positive RSV test within approximately 2 days of hospital admission (primary) or (2) a new onset of respiratory symptoms in an already hospitalized subject, with an objective measure of worsening respiratory status and positive RSV test (nosocomial). Primary and nosocomial RSV hospitalization are further defined below.

Primary RSV Hospitalization

RSV diagnostic testing will be performed on respiratory secretions obtained within approximately 2 days before or after admission for subjects hospitalized for any respiratory infection (upper or lower respiratory tract). If the RSV diagnostic test (performed centrally via RT-PCR) is positive, the hospitalization will be classified as a primary RSV hospitalization. Deaths that can be demonstrated as caused by RSV (by autopsy or clinical history and virologic evidence) will also be considered as primary RSV hospitalization endpoints.

Nosocomial RSV Hospitalization

Subjects hospitalized for a respiratory illness or non-respiratory illness whose RSV diagnostic test is negative may develop nosocomial RSV illness during the study.

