If signs (such as retractions, rhonchi, wheezing, crackles or rales) of a new lower respiratory illness occur during a hospitalization, whatever the reason for hospitalization, and there is an objective measure of worsening respiratory status (that is, new requirement for supplemental oxygen, increase in supplemental oxygen requirement from prior to the onset of symptoms, or need for new or additional mechanical ventilation), a specimen will be collected within approximately 2 days from worsening of respiratory status for RSV diagnostic testing by the central laboratory. For any subject who is hospitalized for a respiratory infection (upper or lower respiratory tract), the subject must return to his/her baseline respiratory status or be clearly resolving the preceding respiratory illness before a subsequent respiratory deterioration for a nosocomial RSV hospitalization event can be determined.

If the RSV diagnostic test (performed centrally via RT-PCR) is positive, the subsequent hospital days will count as a nosocomial RSV hospitalization. The days of RSV hospitalization will be counted beginning with the start of the respiratory deterioration that resulted in the RSV diagnostic test.

RSV LRTI Outpatient Events

Subjects who seek outpatient medical attention, including ER and urgent care visits, for an LRTI should have respiratory secretions obtained within approximately 2 days after the initial healthcare provider assessment.

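### SAP 3.6.1 starts a fatal hospital stay at admission even when the event is nosocomial, and does not say how days are counted when two LRTI events share one admission (minor)

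*SAP*

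**What the plan says.** Three sentences in SAP 3.6.1 define hospital days.

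- General rule: "Duration of each hospitalization will be calculated from the admission or deterioration date to discharge date".
- In-hospital death with a missing discharge date: "the duration of that hospital stay will be calculated from admission to the minimum of {Death Date, End-of-Study Date", with the data cutoff date for the primary analysis as the third candidate end date.
- Aggregation: "Total duration of hospitalization is the cumulated days of each hospital stay throughout the reporting time-period".

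The same section defines two tables that use these durations. One reports "overall HRU for all medically attended LRTI (protocol defined, non-protocol defined, RSV, non-RSV" events together. The other covers protocol-defined medically attended RSV LRTI. It takes over the conventions of the first and adds, for the respective events, the condition that "events and the HRU must occur during the event being summarized" for a use to count.

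Protocol 4.3.1.1 defines when a nosocomial event can arise: "Subjects hospitalized for a respiratory illness or non-respiratory illness whose RSV diagnostic test is negative may develop nosocomial RSV illness during the study". For the count of days it says: "The days of RSV hospitalization will be counted beginning with the start of the respiratory deterioration that resulted in the RSV diagnostic test". It makes no exception for a child who dies.

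**The concern.** The general rule offers two start dates because there are two kinds of inpatient event. A primary hospitalization starts when the child is admitted. A nosocomial one starts when a child already in hospital deteriorates. The death sentence keeps only the first start date, so for a fatal nosocomial event the SAP disagrees with its own preceding sentence and, when the event is RSV, with the protocol.

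The second matter is a gap. A child may be admitted with an RSV-negative LRTI and later, in the same stay, develop nosocomial RSV. Both events belong in the all-LRTI table. The SAP neither closes the first interval at deterioration nor says that shared days count once.

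What is at stake is the hospital-day summary by treatment group. Duration is described by mean, median, SD, minimum and maximum among children with at least one stay, so one long stay can move the mean and set the maximum. The primary safety endpoint and the incidence of RSV LRTI and RSV hospitalization do not use these durations.

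**Working it through.** The plan states no hospital-day figure, so there is none to reproduce. The check is date arithmetic on the rules as written. All dates are assumed.

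**Notation.** A = admission, d = deterioration, D = discharge, X = death. Duration = end minus start. X is taken as the earliest of the three candidate end dates.

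**1. Fatal nosocomial stay, no discharge date**

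- Death sentence in SAP 3.6.1: X − A.
- Start at deterioration (the nosocomial start date in the SAP's general rule, and the protocol's for RSV): X − d.
- Excess: (X − A) − (X − d) = d − A.

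| A, d, X (assumed) | SAP death sentence | From deterioration | Excess |
|---|---|---|---|
| 1, 4, 8 | 8 − 1 = 7 | 8 − 4 = 4 | 3 |
| 1, 6, 15 | 15 − 1 = 14 | 15 − 6 = 9 | 5 |
| 1, 21, 31 | 31 − 1 = 30 | 31 − 21 = 10 | 20 |

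Counting both end days would add 1 to each duration and leave the excess unchanged.

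Whether the excess is an error depends on the table and on the reason for admission.

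- *All-LRTI table, admitted for a reason other than LRTI:* the days from A to d precede any LRTI. The death sentence gives a wrong duration.
- *All-LRTI table, admitted with an LRTI:* the whole stay is LRTI-related, and X − A is the right total.
- *RSV-specific table:* the death sentence, carried over as a convention, gives X − A. The during-the-event condition gives X − d. The SAP issues two instructions for the same child.

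**2. RSV-negative LRTI admission, then nosocomial RSV, child discharged**

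The all-LRTI total can be read in three ways.

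- Two records added: (D − A) + (D − d).
- One stay, started at admission: D − A.
- One stay, started at deterioration: D − d.

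| A, d, D (assumed) | Two records added | One stay from A | One stay from d |
|---|---|---|---|
| 1, 4, 8 | 7 + 4 = 11 | 7 | 4 |
| 1, 6, 15 | 14 + 9 = 23 | 14 | 9 |
| 1, 15, 22 | 21 + 7 = 28 | 21 | 7 |
| 1, 21, 31 | 30 + 10 = 40 | 30 | 10 |

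Only D − A equals the time spent in hospital. The SAP does not say which reading applies. The RSV-specific table is not exposed to this overlap, because the RSV-negative admission is not one of its events.

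**The case against.** A reader might infer that the SAP counts the same days twice and that hospital-day totals are therefore wrong. The documents do not support that. The aggregation sentence adds up hospital stays, and one continuous admission is naturally one stay; on that reading nothing is double counted. Protocol 4.3.1.1 says that, after a positive test, the days that follow count as the nosocomial hospitalization. That can be read as reassigning those days, not as adding them again. SAP Table 2 accepts a new LRTI hospitalization only after the previous adverse event has resolved, which would often prevent a second event. This objection stands against any claim that double counting is prescribed. It does not remove the gap: Table 2 defines events and not durations, and even the one-stay reading leaves the start date open.

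On the fatal case, the during-the-event condition already protects the RSV-specific table in part. That also stands, and it narrows the clear error to the all-LRTI table and a child not admitted for LRTI. It does not make the death sentence consistent with the text around it.

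SAP section 1 leaves table specifications to a separate statistical programming plan, which is not available here. That plan may settle the overlap question. To correct the fatal case it would have to depart from the SAP as written.

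Two further inferences should be resisted. One is a shift in an arm's mean obtained by dividing assumed excess days by the RSV hospitalizations expected at the 1.9% planning rate. That rate describes RSV hospitalizations, not nosocomial or fatal ones. The all-LRTI table, where the clear error lies, has other denominators that the documents do not give. The other is to extend the point to ICU stay, respiratory support and oxygen. The SAP measures these from their own start dates, so the switch between admission and deterioration does not arise.

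**Conclusion.** The point holds in a narrow form. The death sentence in SAP 3.6.1 conflicts with the sentence before it and, for nosocomial RSV, with protocol 4.3.1.1. It gives a wrong duration when three things coincide: admission for a reason other than LRTI, a nosocomial LRTI, and death in hospital with no discharge date. The excess is d − A, which was 3 to 20 days in the assumed examples. In the RSV-specific table the same sentence conflicts with the during-the-event condition. The overlap within one admission is undetermined; it is not a demonstrated double count.

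The severity is minor. The summary is exploratory and descriptive, and the cases are likely to be rare. The documents give no number of nosocomial or fatal cases, so no effect on an arm's mean can be calculated from them.

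**What to change.** Make two changes in SAP 3.6.1.

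1. In the in-hospital-death sentence, start the stay at the admission date for a primary hospitalization or the deterioration date for a nosocomial one, so that it matches the general rule and protocol 4.3.1.1.
2. State that in the all-LRTI total the calendar days within one admission count once per child. For an RSV-negative LRTI admission followed by nosocomial RSV this gives D − A. It also keeps the count from admission for a child admitted with an LRTI who later dies of a nosocomial event, which the first change alone would leave open.

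The cost is two sentences and a small programming change. No new data are needed.
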